1.0 PROTOCOL SUMMARY AND/OR SCHEMA

[figure not shown]
Primary Objective: To compare the efficacy of linear aerobic training versus nonlinear aerobic training, relative to progressive stretching (attention-control group), on exercise capacity (VO_{2peak}) in women with operable breast cancer following the completion of primary adjuvant therapy.

Design: A total of 174 women with histologically confirmed operable breast cancer, meeting the eligibility criteria defined in Section 6.0, will be randomized to one of the following three arms in a 1:1:1 ratio ($n=59/\text{group}$): **Arm A:** supervised linear aerobic training, **Arm B:** supervised nonlinear aerobic training, or **Arm C:** progressive stretching (attention-control group) (see **Figure 1**).

This randomized controlled trial (RCT) is a continuation of a clinical trial initiated and conducted at Duke University Medical Center (DUMC) in Durham, NC by the principal investigator, [name]. The trial was suspended at DUMC (protocol-independent) due to change of the PI's institution. At the time of trial suspension, a total of 115 participants had been randomly allocated to three study groups: $n=38$ in Arm A, $n=39$ in Arm B, and $n=38$ in Arm C. Of these 115 participants, 109 successfully completed all study procedures, and 6 participants were lost to follow-up.

At MSK, 59 participants will be enrolled and randomized until the target enrollment of $n=174$ is met. Twenty participants will be randomized to Arm A; 19 to Arm B; and 20 to Arm C. At the end of the trial, data will be analyzed for the pre-planned target sample size ($n=174$).

Figure 1: Study Schema

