14.3 Primary and Secondary End Point Analyses

14.3.1 Primary End Point Analysis: The primary objective will be to compare the effects of supervised linear aerobic training (Arm A) versus supervised nonlinear aerobic training (Arm B), relative to progressive stretching (attention-control group) (Arm C), on VO_{2peak} in women with operable breast cancer following the completion of primary adjuvant therapy.

An intent-to-treat statistical analysis will be conducted. Baseline characteristics will be compared using the Fisher exact test for categorical variables or a Wilcoxon rank sum test for continuous variables. The primary end point comparison will be analyzed using a multiple regression model to test for differences among and between the study arms in VO_{2peak} from baseline to the follow-up assessment (Week 17). The regression model will include the stratification factors [i.e., treatment with chemotherapy (yes vs. no) and current treatment with endocrine therapy (yes vs. no)].

In the absence of evidence to the contrary, multiple imputation strategies for missing Week 17 VO_{2peak} data will be performed assuming data were missing at random using logistic regression. Results will be aggregated over 20 imputed sets using the variance formula by Rubin. In addition, a per-protocol analysis will be performed using a multiple regression model to test for differences among and between the study arms in VO_{2peak} from baseline to the follow-up assessment (Week 17) on the basis of exercise adherence to the supervised aerobic training sessions (<80% versus ≥80%). In the event that groups are unbalanced on medical or demographic characteristics at baseline, we will also perform a sensitivity analysis that includes these factors in the model.

14.3.2 Secondary End Point Analyses: As for the primary end point, the intention-to-treat principle will be employed for analysis of all secondary end points. Multiple regression models will be used to test for differences among and between the study arms in secondary end points from baseline to the follow-up assessment (Week 17). The regression model will include the baseline value of the end point, as well as any other baseline characteristics that are not balanced between groups. All secondary end points are continuous.

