16.2 Role of Duke University Medical Center (DUMC)

The current trial is a single-site, phase II trial comparing the effects of a standard aerobic training prescription approach versus a novel aerobic training prescription approach in women with operable breast cancer following the completion of primary adjuvant therapy. However, this trial represents a continuing effort that was first initiated at DUMC approximately 5 years ago by the principal investigator, [name]. Prior to his appointment at MSK in February 2014, [name] was a principal investigator at DUMC. During his tenure there, [name] secured a 5-year R01 grant from the National Cancer Institute to conduct the present study. During trial conduct, [name] accepted a position at MSK and hence the protocol was closed to accrual. Participants on trial completed all study-related procedures but the study was closed to new patient enrollment.

IRB correspondence: All local IRB correspondence for DUMC that is initiated after the MSK protocol is open to accrual should be submitted to MSK. This includes but is not limited to approvals for amendments and continuing reviews as noted below. All other correspondence should be submitted to the local IRB according to local guidelines.

Amendments: Each change to the protocol document must be organized and documented by MSK and first approved by the MSK IRB/PB. Upon receipt of MSK IRB/PB approval, Ex-Onc research staff will immediately distribute all non-expedited amendments to DUMC for submission to the local IRB.

DUMC must obtain approval for all non-expedited amendments from their IRB within 90 calendar days of MSK IRB/PB approval.

Continuing Review Approval: The Continuing Review Approval letter from the DUMC IRB and the most current, approved version of the informed consent form should be submitted to MSK within 7 days of expiration.

Document maintenance: The MSK PI and the DUMC PI will maintain adequate and accurate records to enable the implementation of the protocol to be fully documented and the data to be subsequently verified.

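### The pooled analysis of the DUMC and MSK cohorts has no site term, which gives up a modest and unknown amount of precision that one covariate would recover

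*Combined protocol and SAP*

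**What the plan says.** Section 1.0 explains that the trial began at DUMC, where 115 women were randomized (38 to Arm A, 39 to Arm B, 38 to Arm C) before accrual stopped. It continues at MSK with 59 more: "Twenty participants will be randomized to Arm A; 19 to Arm B; and 20 to Arm C". The two cohorts are then combined: "At the end of the trial, data will be analyzed for the pre-planned target sample size", which is 174.

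For the primary end point, Section 14.3.1 states "The regression model will include the stratification factors", which it identifies as chemotherapy and current endocrine therapy. For the secondary end points, Section 14.3.2 states "The regression model will include the baseline value of the end point, as well as any other baseline characteristics that are not balanced between groups". The per-protocol analyses are organised by adherence, and the sensitivity analyses add medical or demographic characteristics found to be unbalanced. Multiple imputation is specified without a list of predictors. Site appears in none of these, and Section 15.3 does not list it as a stratification factor.

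Section 16.2 (Role of DUMC) says "The current trial is a single-site, phase II trial", and goes on to describe the DUMC phase.

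**The concern.** The cohorts come from different institutions and different years. Section 16.3 gives DUMC ethics approval in March 2010 and the 115 participants as of September 2013. Section 16.2 places the investigator's move to MSK in February 2014. Laboratory, supervising staff and referral population may all differ, and Section 12.1 itself describes VO2peak measurement as materially variable.

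Site is balanced across arms within each cohort, so it behaves much like a stratification factor. When a balanced factor is related to the outcome but left out of the model, the arm contrast is essentially unaffected. The factor's variance still sits in the residual, so standard errors come out larger than necessary. The plan already adjusts for its two declared stratification factors, and the same reasoning applies to site.

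The clauses on unbalanced characteristics would not bring site in. They are triggered by imbalance between arms, and site is almost perfectly balanced by plan. At stake are some power for A versus B, the tighter of the two primary comparisons, and the avoidance of a post hoc decision on whether to adjust.

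**Working it through.** **Inputs.** From Section 1.0: 115 DUMC and 59 MSK participants, with arm counts 38/39/38 and 20/19/20, so 58 per arm. From Section 14.2: A–B difference 2.5, B–C difference 4.0, SD of change 4.0 mL/kg/min in every arm, two-sided alpha 0.025, stated A–B power 86%. Assumed, because the documents give no value: d, the DUMC–MSK difference in mean VO2peak change, from 0 to 4 mL/kg/min.

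**Step 1: reproduce the plan's figure.** The standard error is 4.0 × √(2/58) = 0.743, and 2.5/0.743 = 3.37. Power is 86.2% by noncentral t with 114 df, 86.4% with 171 df (three-arm model) and 87.0% by normal approximation. The stated 86% reproduces.

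**Step 2: variance left in the residual.** With p = 115/174, p(1 − p) = 115 × 59/174² = 0.224. Omitting site leaves v = 0.224 × d² in the residual.

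**Step 3: A–B power if 4.0 is the within-site SD.** Without site, the SD used is √(16 + v) with 171 df. With site, it is 4.0 with 170 df.

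| d | v | SD without site | Interval widening | Power without site | Power with site |
|---|---|---|---|---|---|
| 0 | 0 | 4.00 | 0% | 86.4% | 86.4% |
| 1 | 0.22 | 4.03 | 0.7% | 85.9% | 86.4% |
| 2 | 0.90 | 4.11 | 2.8% | 84.4% | 86.4% |
| 3 | 2.02 | 4.24 | 6.1% | 81.8% | 86.4% |
| 4 | 3.59 | 4.43 | 10.6% | 78.2% | 86.4% |

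B–C is hardly affected. Even at d = 4, 4.0/(4.43 × √(2/58)) = 4.86, and power stays above 99%.

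**Step 4: A–B power if 4.0 is the total SD.** Power without site is then 86.4% throughout. With site, the SD is √(16 − v) = 3.97, 3.89 and 3.74 for d = 1, 2, 3, and power is 86.9%, 88.4% and 90.9%. The gain is similar in size to Step 3, but the level depends on this reading of the SD.

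**Step 5: validity.** The MSK share is 20/58 in Arm A and 19/58 in Arm B, so the shift in A–B is (20/58 − 19/58) × d = 0.017d, or 0.05 mL/kg/min at d = 3. A simulation of 40,000 trials per setting, using the planned counts and within-site SD 4.0, gave rejection rates under the null without site of 0.023 at d = 1, 0.023 at d = 2 and 0.014 at d = 4, against the nominal 0.025. The test becomes conservative. Simulated power without site was 85.3%, 84.0% and 77.8% at d = 1, 2, 4, in line with the table.

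**Step 6: what a site interaction could show.** The standard error of the A–B by site interaction is 4.0 × √(1/38 + 1/39 + 1/20 + 1/19) = 1.57. Its 95% interval is about ±3.1, wider than the 2.5 target effect. The difference detectable with 80% power is about 2.8 × 1.57 = 4.4.

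**The case against.** The strongest reply is that nothing invalid is planned and the benefit is speculative. d is a difference in mean *change*, so a constant offset between laboratories cancels within each woman. Section 14.2 assumes only 1.5 mL/kg/min for the whole advantage of linear training over control, so a d of 2 or 3 would exceed that effect. At d = 1 the loss is half a percentage point. This stands, and it is why the point is a refinement.

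Five stronger readings are tempting and are not supported:

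- A reader might infer that the pooled result is biased or its error rate inflated. Step 5 shows neither.
- A reader might infer that the planned intervals are certainly too wide. That depends on d, which is unreported.
- A reader might infer that device-based secondary end points (arterial stiffness, FMD, echocardiography, DEXA) are the most exposed. Their models include the baseline value, which absorbs much of a persistent device offset, and the documents do not describe DUMC's equipment.
- A reader might infer that missing values at one site would be filled from the other site's level. Section 14.3 lists no imputation predictors. A model without site would draw toward a pooled level, and DUMC losses were only 6/115 (Section 1.0) or 9/115 (Section 16.3), about 5% to 8%.
- A reader might infer that the cohorts were randomized from separate lists. The documents do not say whether the DUMC list was continued, and 20/19/20 is simply what completes 58 per arm. The argument needs only the stated balance.

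Nor does the single-site wording conceal anything. The same section goes on to describe the DUMC phase, and the phrase plausibly refers to the MSK continuation.

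**Conclusion.** The omission is confirmed on the text: no stated model includes site. The consequence is lost precision, with no inflation of type I error and a negligible shift in A–B. With 4.0 as the within-site SD, the A–B power loss is about 0.5 points at d = 1, 2 points at d = 2 and 5 points at d = 3. The alternative reading, in which a site term lifts power to as much as 91%, requires that 4.0 already contain the DUMC–MSK difference. Section 14.2 attributes that SD to earlier work in post-therapy patients and gives no ground for assuming so.

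Both readings favour a site term whenever d is not zero, and at d = 0 the term costs practically nothing. Site and calendar period cannot be separated here, so the term would capture a combined cohort effect. Severity is low: an optional refinement with a modest expected gain.

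**What to change.** Prespecify a fixed cohort indicator (DUMC versus MSK) in the primary, secondary and per-protocol models, and name it among the predictors in the imputation model.

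Report arm means and arm differences by site descriptively. State that the interaction is too imprecise to establish that the A–B effect is consistent across sites, so that a non-significant result is not read as reassurance.

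Reword the single-site description in Section 16.2 so that it agrees with the pooled two-site analysis in Section 1.0.

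The cost is SAP wording and one degree of freedom. Site is already known for every participant, and A–B power stays at 86.4% if the sites do not differ.

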2.1 OBJECTIVES AND SCIENTIFIC AIMS

2.1 Primary Objective

To compare the effects of supervised linear aerobic training versus supervised nonlinear aerobic training, relative to progressive stretching (attention-control group), on $\text{VO}_{2\text{peak}}$ in women with operable breast cancer following the completion of primary adjuvant therapy.

2.2 Secondary Objectives

- To compare the effects on resting and exercise cardiac function;
- To compare the effects on pulmonary function;
- To compare the effects on arterial stiffness;
- To compare the effects on endothelial function;
- To compare the effects on body composition;
- To compare the effects on patient-reported outcomes (e.g., quality of life, fatigue) ;
- To collect and bank blood samples for future correlative studies; and
- To assess and compare the safety of supervised aerobic training.

3.0 BACKGROUND AND RATIONALE

3.1 Indication

The intended indication for supervised linear or nonlinear aerobic training is the treatment of impaired exercise capacity (i.e., global cardiovascular function) in patients with operable breast cancer following the completion of primary adjuvant therapy.

3.2 Background and Rationale

Exercise capacity is one of the most important indicators of health and longevity in humans.^{1,2} The capacity of mammals to transport oxygen (O_2) from the atmosphere to the muscle mitochondria determines an individual's exercise capacity.³ Maximal or peak oxygen consumption ($\text{VO}_{2\text{peak}}$) provides the gold standard measurement of exercise capacity and is strongly and inversely related to risk of death.⁴⁻⁸

The importance of exercise capacity following a breast cancer diagnosis has received limited attention.⁹ However, over the past decade, there has been increased recognition and acceptance of the importance of therapy late effects (e.g., cardiovascular disease, type 2 diabetes, fatigue, deconditioning) as a major but underappreciated area in breast cancer management.¹⁰ Poor exercise capacity may be of central importance for certain adverse late effects — including impaired left ventricular ejection fraction, elevated cardiovascular disease (CVD) risk profile, poor quality of life, and fatigue — following the completion of adjuvant therapy for operable breast cancer.¹¹⁻¹³ Further, recent landmark observational studies report that regular self-reported physical activity (e.g., brisk walking, ≥ 30 minutes/day, 5 days/week), a major determinant of exercise capacity, is associated with 30% to 50% reductions in breast cancer-specific mortality and all-cause mortality following the completion of adjuvant therapy.^{14,15}

Despite its importance, women with breast cancer have markedly reduced exercise capacity. In a series of studies by our group, we observed that VO_{2peak} was approximately 30% below that of age-matched *sedentary* healthy women up to three years following the completion of adjuvant therapy.^{11,12,16} The precise causes of the significant and marked impairments in VO_{2peak} are not known but likely are a consequence of direct cytotoxic therapy-associated injury to the cardiovascular system (e.g., impairments in the organ components that govern VO_{2peak}) together with lifestyle perturbations (e.g., deconditioning and weight gain) that we have termed the ‘multiple hit’ hypothesis.⁹

A growing number of research groups have investigated the efficacy of supervised exercise training interventions (aerobic, resistance, or combination training) to counteract therapy-induced poor exercise capacity both during and following the completion of adjuvant therapy. Overall, the current literature base indicates that supervised exercise training is a safe and feasible adjunctive therapy associated with significant improvements in objective measures of exercise capacity (including VO_{2peak} as measured by a symptom-limited cardiopulmonary exercise test (CPET)) as well as a broad range of PROs.¹⁷ Preliminary data also indicate that exercise training, particularly aerobic training, may cause favorable improvements in circulating metabolic hormone concentrations in women with operable breast cancer following the completion of adjuvant therapy.^{18,19}

Although much progress has been made over the past 20 years, the format and intensity of exercise training required to induce optimal improvements in VO_{2peak} and other pertinent outcomes in women with breast cancer have not been investigated. The American College of Sports Medicine (ACSM) convened a panel of experts to review the available evidence supporting exercise prescription guidelines for cancer survivors.²⁰ The panel concluded that cancer patients follow the 2008 Physical Activity Guidelines for Americans (≥ 150 minutes/week of moderate-intensity, or ≥ 75 minutes/week vigorous-intensity aerobic exercise or an equivalent combination of moderate- and vigorous intensity aerobic exercise), yet few studies have tested this empiric prescription in a formal randomized controlled trial.

Moreover, the most important methodological consideration when conducting any exercise training trial is that the exercise prescription closely adheres to the fundamental principles of training (i.e., individualization, specificity, progressive overload, and rest/recovery). Alarming, two recent systematic reviews found that the vast majority of exercise training trials in the oncology setting did not comply with these fundamental principles.^{21,22} Rather, the vast majority of trials investigate the effects of exercise training prescriptions in which the majority of training sessions are performed at the same intensity and duration; thus, training volume remains constant across the entire intervention — this is known as a linear exercise training prescription. This is problematic because as VO_{2peak} improves, the adaptation from an identical exercise stimulus diminishes; therefore, there is an insufficient stimulus to induce further physiologic adaptation.

In contrast, in nonlinear exercise training prescriptions, the intensity, duration, and occasionally, the frequency, of training sessions are sequenced in such a fashion that training volume is continually increased across the entire program (i.e., the principle of progressive overload). This approach also adds important variety to the prescription that not only continually alters the exercise ‘stress’ (to optimize adaptation), but can also stimulate

participant interest and motivation. In addition, training intensity is sequenced such that higher intensity or higher volume training is followed by lower intensity (recovery) training and rest days to optimize adaptation (i.e., the principle of rest and recovery). Our group has previously demonstrated the safety, feasibility, and potential efficacy of a nonlinear exercise training approach in several cancer populations.²³⁻²⁶ However, no study to date has compared whether a nonlinear exercise training approach is superior to the traditional, linear training approach in patients with cancer.

Against this background, we designed the EXCITE trial, a randomized controlled trial comparing the effects of supervised linear aerobic training versus nonlinear aerobic training in women with operable breast cancer following the completion of primary adjuvant therapy.

3.3 Effects of Aerobic Training on Exposure to Other Conventional/Novel Anticancer Therapies

There is no clinical data on the effect of aerobic training (or progressive stretching) on the therapeutic index of anticancer agents used in the management of breast cancer. Eligible subjects in this trial will not be receiving any primary adjuvant therapy, but they may potentially be receiving endocrine therapy. All clinical studies to date have focused on the effects of exercise training interventions to prevent and/or mitigate the psychosocial and/or physiological side-effects of cancer therapy; whether exercise training influences the pharmacodynamics (PD) or pharmacokinetics (PK) of anticancer therapy has not been investigated.

3.4 Effects of Conventional/Novel Anticancer Therapies on Aerobic Training

Our group, as well as others, have demonstrated that different forms of anticancer therapy cause unique and varying degrees of damage to various components of the cardiopulmonary system (heart-lung-blood-muscle axis). Collectively, these effects lead to significant and marked declines in global cardiopulmonary function, manifest as poor exercise tolerance (decreased VO_{2peak}). A major rationale for this trial is to determine the optimal aerobic training prescription approach to reverse this phenotype in women with operable breast cancer.

4.1 OVERVIEW OF STUDY DESIGN/INTERVENTION

4.2 Design

This open-label, three-arm randomized controlled trial will compare the effects of supervised linear aerobic training versus supervised nonlinear aerobic training, relative to progressive stretching (attention-control group), in women with operable breast cancer following the completion of primary adjuvant therapy. The primary endpoint is VO_{2peak} , as measured by a symptom-limited cardiopulmonary exercise test (CPET).

The study periods will include screening, study intervention, and follow-up assessments.

4.3 Intervention

Following eligibility confirmation participants will be randomized to one of three study arms. All participants will undergo their first aerobic or stretching training session at MSK within a maximum of 14 days following randomization.

Participants will perform structured supervised aerobic training as part of clinical trial participation. Exercise performed outside the structured sessions (i.e., contamination) will be assessed via self-report of exercise behavior. For ethical reasons, we will not instruct participants not to exercise outside the structured sessions, but we will encourage participants to maintain their level of exercise behavior prior to the initiation of the trial.

At Weeks 4, 8, and 12, all participants will perform a fasting research blood draw. Participants assigned to the nonlinear aerobic training (Arm B) will also perform a CPET at midpoint. The purpose of this test is to re-assess exercise capacity to re-prescribe aerobic training to ensure progressive cardiovascular adaptation across the entire intervention period.

